Objectives	Primary objective Assess the rates of BSI from the use of 3CBs (e.g., SmofKabiven [®] , Kabiven [®] , others) compared to hospital compounded bags (HCBs) in patients requiring PN in Spanish hospitals
	 Secondary objectives Determine the extent of treatment requirement in patients receiving 3CBs compared to hospital compounded bags Assess mortality rate in patients receiving 3CB compared to patients receiving HCBs Evaluate the influence of additions made to the PN bags on BSI rates Assess the effect of manual versus automated compounding on BSI rates Evaluate the rate of PN-associated adverse events in patients receiving 3CBs compared to HCBs, including sepsis, organ failure, metabolic impairment, hepatic dysfunction and electrolyte imbalance Assess the achievement of the nutritional target in patients receiving 3CBs compared to HCBs
Investigational sites	Approximately 10 sites using 3CBs and/or HCBs
Study design	Retrospective observational data retrieval in a two-step design: In step 1, data from 30% of the target patient number will be obtained from the investigational sites to evaluate study feasibility and perform an interim analysis assessing statistical power.In step 2, the study will be continued by documenting further 70% of patients if the statistical power is > 60%.
Observational drug	Any PN administered in 3CBs, containing all three major macronutrients (glucose, amino acids, lipids)
Comparator	Hospital compounded PN bags containing all three major macronutrients
Patients	Adult hospitalized patients receiving PN in Spain, treated on any ward and by any medical discipline within the hospital (intensive care unit, normal ward; surgery, non-surgery)

Outcome parameters Primary outcome parameter

 BSI only with concomitant antimicrobial treatment (bacteria and/or candida), thereby excluding patients with contaminations

Secondary outcome parameters

- Rate of peripheral line associated BSI
- Rate of central line associated BSI
- Single organ failure, multiple organ failure
- Mortality
- PN-related adverse events of special interest: metabolic impairment (hyperglycemia, hypertriglyceridemia), hepatic dysfunction (cholestasis: transaminases, gamma-glutamyl transferase, alkaline phosphatase, bilirubin), electrolyte imbalance (sodium, potassium, chloride, calcium, phosphate, bicarbonate)
- Changes in prealbumin, C-reactive protein
- Achievement of caloric target (hypo-, hyperalimentation)

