- Extent of treatment requirement: Hospital length of stay, ICU length of stay, antibiotics, antimycotics, vasopressors and mechanical ventilation

These parameters will be documented for the multivariate analysis - if available - and the discussion. These are not outcome parameters:

- Demographic data: gender, age, weight (BMI)
- Admission type: elective, emergency, transferral
- Reason for hospital admission: leading diagnosis
- Reason for ICU admission: surgical, medical, trauma
- Primary disease
- Duration of hospitalization before venous catheter (VC) placement and PN
- Type of venous access: central, peripheral
- VC insertion and maintenance according to "Bacteremia Zero" protocol
- Type of hospital compounding: automated, manual
- VC related influence: number of VC; number of lumen of VC; site of VC placement (jugular, subclavian, femoral); insertion of VC in ER, OR, ICU; clinical experience of staff placing and handling VC and PN; duration of VC; duration of PN and duration between VC placement and PN; SOP for hygiene in place (cap, mask, sterile gloves sterile full body drape)
- Indication for PN
- Percentage of PN (supplemental PN, total PN)
- Omega-3 fatty acids and glutamine as active ingredients

- Additions of vitamins, trace elements and/or electrolytes to PN bag
- Addition to PN bag made under sterile conditions in the pharmacy, or on the ward
- Co-morbidities: cancer, malabsorption, pancreatitis, liver failure, renal failure, diabetes, malnutrition (SGA), gastrointestinal disorder
- Enteral, oral nutrition, oral nutritional supplements
- Antibiotic and antimycotic treatment (number, duration, antibiotic free days)
- Availability of a Nutrition Support Team at the center
- Hospital characteristics: region, teaching status, urban/ rural, number of beds
- APR-DRG severity of illness
- APACHE II score or SAPS II score

Inclusion criteria

General:

- Adult patients \geq 18 years
- Hospitalized between 1. January 2014 and 31. December 2015

Study-specific:

- PN for at least three consecutive days
- PN as 3CBs or hospital compounded, containing all three major macronutrients
- complete medical record regarding treatment information, PN administration details and, if applicable, adverse events

Exclusion criteria

General

Prior participation in this study

Study specific

- BSI at admission to the participating hospital (not hospitalacquired), i.e., prior to the 3rd calendar day of admission
 - where day of admission is calendar day 1

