- Immunosuppression due to concomitanttherapy (e.g. immunosuppressive therapy due to transplantation, use of glucocorticoids)or disease (e.g. HIV, leukemia)
- persisting vascular access (port, shunts for dialysis) used during PN episode
- femoral venous placement of central venous line
- burns (irrespective of severity), extensive skin injuries (e.g., Lyell's disease)
- chemo-/ radiotherapy during hospital admission period or up to 3 months before hospital admission
- change of PN delivery method during study period, e.g., from compounding to 3CBs (change of dosing and/or frequency during the observational period is allowed)

Sample size	The sample size must allow the comparison of BSI rates associated with three chamber bags with those associated with hospital compounded bags. Due to the high variability among studies reported in the literature, a mean scenario is considered based on the incidence of BSI infections reported in Spain [Bonet 2005; Aguilella 2012], i.e., an overall incidence of BSI of 12.3% with a difference between the groups of 3% (± 1.5%). Samples size are estimated assuming incidence rates of BSI in MCB of 10.8% and 13.8% in hospital compounded PN, respectively. A sample of 1891 patients per PN type (3782 patients in total) is required taking into account a significance level of 0.05, the influence of the interim analysis on statistical power, and a statistical power of 0.80.
Statistical analysis	Interim analysis: The study is run in a 2 stage group sequential design with an interim analysis (IA) after acquiring 30% of the total sample size. This allows a premature discontinuation if BSI rates and their difference, i.e., the actual power of the study, are substantially lower than planned. The study will be terminated after the IA if the conditional power based on the IA results will be smaller than 60%.

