	Final analysis: Baseline demographics, co-morbidities and hospitalization characteristics will be reported descriptively by means of standard deviations and medians with ranges for continuous variables and by counts and percentages for categorical variables. Incidence rates for BSI will be reported by treatment group. Multivariate logistic regression will be used to create a model to estimate the risk of BSI. The model will be adjusted for covariables as risk factors, potential confounders, baseline differences, etc. As variable-selection method correlations will be calculated for the rough selection and then backward elimination selection will be applied in the logistic regression model with a significance level of 10%. The risk of BSI will be reported as adjusted odds ratios with 95% confidence limits. For secondary/ further variables multivariate regression models will be used.
Observation period	Length of stay at the participating hospital
Planned start and end	Data retrieval for step 1: September 2016 – January 2017 Data retrieval for step 2: March – June 2017
Principal investigator	[name] PhD Madrid, Spain

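### Excluding every patient whose bag type changes after PN has started deletes BSIs that occurred on the first bag type, and can bias the comparison in either direction

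*Combined protocol and SAP*

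**What the plan says.** The study-specific exclusion criteria remove patients with a "change of PN delivery method during study period, e.g., from compounding to 3CBs (change of dosing and/or frequency during the observational period is allowed"). Dose and frequency may vary; bag type may not. The term study period is not defined in that criterion: it could mean the 2014–2015 window, the PN episode or the hospital stay.

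The surrounding sections read as follows:

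- Primary objective: "Assess the rates of BSI from the use of 3CBs", compared with hospital compounded bags (HCBs).
- Primary outcome: "BSI only with concomitant antimicrobial treatment (bacteria and/or candida), thereby excluding patients with contaminations".
- Inclusion: "PN for at least three consecutive days".
- Observation period: "Length of stay at the participating hospital".
- Final analysis: "Incidence rates for BSI will be reported by treatment group", followed by a logistic regression of BSI with adjusted odds ratios.
- Investigational sites: "Approximately 10 sites using 3CBs and/or HCBs", so both bag types may be in use at one site.

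No section ends follow-up at a change of bag, assigns events to the bag in use, counts the excluded switchers by group, or plans a sensitivity analysis that includes them.

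**The concern.** The rule selects patients on something that lies in the future when PN starts. Three records show the effect:

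- 3CB on days 1–10, treated BSI on day 8, compounded bag from day 11: a BSI on 3CB is deleted.
- HCB on days 1–12, treated BSI on day 6, 3CB from day 13: a BSI on HCB is deleted.
- 3CB on days 1–10, no BSI, discharged: kept as a non-event.

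The two deleted events are exactly what the primary objective sets out to count. A long PN course gives more opportunity both for a BSI and for a change of bag, so switchers may carry more events than the patients who stay. If that excess differs between groups, the odds ratio is distorted. If it is the same in both, the odds ratio survives but both rates are understated, which matters because the study rationale names a pharmaco-economic model as the user of these data. The same deletion affects mortality, organ failure and PN-related adverse events.

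**Working it through.** **The plan's own figure.** Sample size section: "Samples size are estimated assuming incidence rates of BSI in MCB of 10.8% and 13.8% in hospital compounded PN", significance level 0.05, power 0.80, 1891 per group. A two-sided comparison of two proportions gives 1881 per group. The ratio 1891/1881 = 1.005 fits a small allowance for the interim analysis, and power at 1891 is 80.2%. The sample size reproduces and is not in dispute.

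**Effect of the exclusion.** Let p be the true BSI risk in a group, a the share of its BSI patients who switch and b the share of its non-BSI patients who switch. After exclusion:

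- observed risk = p(1−a) / [p(1−a) + (1−p)(1−b)]
- odds in that group are multiplied by (1−a)/(1−b)

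The documents give neither a nor b, so all values of a and b below are assumptions.

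**No true effect, p = 13.8% in both groups (the plan's HCB figure), switching in one group only.** For a = 20%, b = 5%:

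- observed risk = 0.138×0.80 / (0.138×0.80 + 0.862×0.95) = 0.1104/0.9293 = 11.9%
- OR = 0.80/0.95 = 0.84
- difference 0.0192; standard error √[(0.138×0.862 + 0.1188×0.8812)/1891] = 0.0109
- chance of a significant result favouring that group = Φ(0.0192/0.01088 − 1.96) ≈ 42%, against 2.5% without the bias

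| a (BSI) | b (non-BSI) | Observed risk | OR | Chance of false significance in that group's favour |
|---|---|---|---|---|
| 15% | 5% | 12.5% | 0.89 | 21% |
| 20% | 5% | 11.9% | 0.84 | 42% |
| 25% | 5% | 11.2% | 0.79 | 67% |
| 20% | 20% | 13.8% | 1.00 | 2.5% |

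Starting from the plan's overall incidence of 12.3%, a = 20% and b = 5% give 10.6% and about 39%.

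**At the planned effect (10.8% vs 13.8%, OR 0.756), a = 20%, b = 5%.**

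| Switching in | 3CB rate | HCB rate | OR |
|---|---|---|---|
| 3CB only | 9.3% | 13.8% | 0.637 |
| HCB only | 10.8% | 11.9% | 0.898 |
| Both equally | 9.3% | 11.9% | 0.756 |

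If non-BSI patients switch more often (a = 5%, b = 15% in the 3CB group), the 3CB rate rises to 11.9%.

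**Link through PN duration.** A day-level simulation assumed PN of 3 days plus a geometric tail (mean 11 days), a BSI hazard of 0.0140 per day (13.8% overall) and a switch hazard of 0.01 per day.

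| Switch hazard after BSI | Observed BSI rate after exclusion | Share of all BSIs deleted although before the switch |
|---|---|---|
| unchanged | 13.1% | 7.1% |
| doubled | 12.2% | 13.2% |
| tripled | 11.5% | 18.5% |

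In the first row the daily hazard ignores BSI, yet 14.8% of BSI patients switch against 9.4% of the others, because long courses carry more of both events.

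**Check of the remedy.** In the unchanged-hazard scenario, keeping switchers but counting BSI only up to the change in a simple proportion gives about 12.8%. That is further from 13.8% than the 13.1% under exclusion, because time at risk is cut short. Events per PN-day up to the change recover 14.0 per 1000 PN-days in all three scenarios.

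**The case against.** A reader might infer that the rule makes 3CBs look better: a 3CB is a fixed formulation, so patients with complications would move to compounded bags and take their BSIs out of the 3CB group. The documents do not support this. The only direction the criterion names is from compounding to 3CBs; BSI-related switching confined to that direction would lower the HCB rate and work against the study hypothesis. With a = 20% and b = 5% in the HCB group only and no true effect, the chance of a falsely significant 3CB advantage is below 0.1%. The plan also records additions of vitamins, trace elements and electrolytes and permits dose and frequency changes, so some changes in need can be met without changing the bag.

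A second tempting reading is that more switching in one group is enough by itself. It is not: removing 20% of one group and 5% of the other, regardless of BSI, leaves 10.8% and 13.8% unchanged.

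Third, the illustrations are crude, while the plan reports adjusted odds ratios and lists PN duration and severity scores as covariates. This has force. With switching in one group only, adjusting for PN duration moves the odds ratio from 0.94 to 1.00 under a constant switch hazard, and from 0.87 to 0.93 when the hazard doubles after BSI. Adjustment can therefore remove the part due to PN duration, but not a direct link between BSI and switching. These covariates are collected only if available and then face backward elimination.

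Finally, some sites may use one bag type only, which limits switching, and a clean exposure is a fair aim. Neither point explains why the switchers and their events go unreported.

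**Conclusion.** The point holds as a conditional one. The plan excludes on a post-baseline event, removes BSIs that belong to the first bag type, and has nothing that would reveal how many were lost or from which group. Bias in the comparison requires that switching be associated with BSI, directly or through PN duration, and that this differ between groups. Under the assumed 20% against 5% in one group, a null effect shows as an odds ratio of 0.84, with about a 42% chance of false significance; the result mirrors if the other group switches. Because no switch rate, reason or dominant direction is given, neither the size nor the sign can be settled from the documents, and a bias towards the hypothesis should not be claimed.

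**What to change.** - Replace the exclusion. Classify each patient by the PN type of the first three consecutive PN days, keep switchers in that group, and state how a change within those three days is handled.
- Record the date and reason of any change and the BSI onset date.
- Run the planned logistic regression on the initial classification over the whole observation period.
- Add an analysis that ends follow-up at the change, using a person-time or time-to-event model (BSI per PN-day). A truncated proportion or a plain logistic model should not be used for this.
- Report the number of switchers and their BSIs by first bag type.

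If the exclusion is kept for the main analysis, the first-bag analysis and that count are the minimum.

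Cost: additional dates and a reason on the data form and one further analysis; the target number of patients does not change. The initial-type analysis attributes some time on the second bag to the first, and ending follow-up at the change may be informative censoring. Presenting both analyses shows how much each matters.

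### The primary BSI model has no days at risk, and total PN duration, a selectable covariate that BSI itself can alter, can bias the bag effect in either direction

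*Combined protocol and SAP*

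**What the plan says.** The hypothesis and the primary objective are both worded in terms of BSI rates, compared between 3CBs and HCBs. The Final analysis text gives the method: "Multivariate logistic regression will be used to create a model to estimate the risk of BSI". The result is an adjusted odds ratio with a 95% confidence interval. Descriptively, "Incidence rates for BSI will be reported by treatment group", with no denominator given.

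The Observation period is "Length of stay at the participating hospital". Inclusion requires three or more PN days in a row and sets no upper limit, so exposure varies between patients.

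On adjustment: "The model will be adjusted for covariables as risk factors, potential confounders, baseline differences, etc". The list of non-outcome parameters includes "duration of VC; duration of PN and duration between VC placement and PN". Of that list the plan says "These parameters will be documented for the multivariate analysis - if available - and the discussion". Covariates are chosen by a correlation screen, after which "backward elimination selection will be applied in the logistic regression model with a significance level of 10" per cent.

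PN duration is therefore a candidate covariate. The plan does not force it into the model and does not say whether PN days are counted only up to the first BSI. It defines no offset, time-to-event model or rate per PN-day. A date of BSI onset is not among the listed parameters.

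**The concern.** A patient on PN for longer has more days on which a BSI can occur. Bag type is not randomised, so the two groups may differ in how long PN lasts. A yes/no analysis without days at risk then mixes the effect of the bag with the effect of time on PN.

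Entering total PN duration as a covariate is the obvious remedy, but it is safe only if BSI does not change PN duration. If a BSI prolongs PN, or leads to PN being stopped, total duration is partly a consequence of the outcome, and conditioning on it distorts the comparison.

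At stake is the main claim that 3CBs lower the BSI rate. The Study rationale says the data will also feed a pharmaco-economic model.

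**Working it through.** **1. The plan's own figure.** Inputs from Sample size: 10.8% and 13.8%, significance level 0.05 (two-sided reproduces the figure), power 0.80. With the pooled-variance formula and mean proportion 0.123:

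n = [1.960·√(2·0.123·0.877) + 0.842·√(0.108·0.892 + 0.138·0.862)]² / 0.030² = 1881 per group.

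The plan states 1891, which gives 80.2% power. The figure reproduces, and the sample size is not affected by this point.

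**2. Assumptions for the range.** No bag effect; the same constant hazard per PN-day in both groups; HCB mean PN of 10 days. The hazard is −ln(1 − 0.138)/10 = 0.1485/10 = 0.01485 per day, or 14.9 per 1000 PN-days. None of the durations comes from the documents.

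**3. Duration left out.** Incidence at d days is 1 − exp(−0.01485·d).

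- d = 10: 13.8%.
- d = 9: 12.5%; OR = (0.125/0.875)/(0.138/0.862) ≈ 0.89. A comparison of 1891 per group is significant about 22% of the time.
- d = 7.7: 10.8%; OR = (0.108/0.892)/(0.138/0.862) ≈ 0.76, significant about 80% of the time.

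The duration ratio that turns 13.8% into exactly 10.8% is ln(0.892)/ln(0.862) = 0.1143/0.1485 = 0.77. PN that is 23% shorter would by itself produce the whole planned 3-point difference.

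**4. Total duration as a logistic covariate.** Simulation with PN durations of 3 days plus a gamma variable, 1891 per group, no bag effect, and 300 to 400 runs per scenario. In repeat runs the odds ratios moved by up to about 0.03 and the rejection percentages by up to about 6 points.

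| Mean PN, 3CB vs HCB (days) | Effect of BSI on PN | Adjusted OR | False rejection |
|---|---|---|---|
| 7.7 vs 10 | none | 0.98–0.99 | 4–6% |
| 7.7 vs 10 | extends PN by 3 days | 1.45 | 88% |
| 7.7 vs 10 | PN stops | 0.53 | 100% |
| 9 vs 10 | none | 1.00 | 4% |
| 9 vs 10 | extends PN by 3 days | 1.14 | 28% |
| 9 vs 10 | PN stops | 0.78 | 72% |
| equal | any of these | about 1.0 | near 5% |

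The direction follows from the mechanism. If BSI prolongs PN, infected patients have long durations because they were infected. The model then overstates the effect of duration and over-corrects in favour of the longer-duration group. If PN stops at BSI, infected patients have short durations, and adjustment makes the shorter-duration group look better still. If 3CB were the longer-duration group, the odds ratios would invert (1/1.45 ≈ 0.69 and 1/0.53 ≈ 1.89).

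Duration passed the 10% elimination threshold in every run, so its retention in the model is no protection.

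**5. Days at risk.** In the 7.7 versus 10 day scenarios, a Poisson model with log PN-days to first BSI as offset gave a rate ratio of about 1.0 with 5–8% rejection.

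**The case against.** The strongest reply is that the plan already handles duration. It records "duration of PN and duration between VC placement and PN" for the multivariate analysis. If BSI leaves PN duration unchanged, covariate adjustment removes the bias, and backward elimination keeps the variable. The proviso about availability is weak for this item, because inclusion requires complete records of PN administration. All of this stands. A reader might infer that the plan ignores PN duration, or that elimination is likely to drop it; the documents and the simulation support neither.

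A reader might also take the 22% and 80% in step 3 as the plan's false-positive rate. They describe an unadjusted comparison, whereas the planned estimate is an adjusted odds ratio.

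The documents also use 'rate' for a cumulative proportion, since the sample size rests on 10.8% and 13.8%. Risk per patient over a stay is a legitimate target, and nothing says the economic model needs a rate per day. That supports keeping the logistic odds ratio. It does not make total PN duration a sound covariate, because it may include days after the event.

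Finally, no PN durations are given, so whether they differ, and in which direction, is unknown. That stands, and it is why the result is a range.

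**Conclusion.** The point holds in this form: the primary model has no days at risk, and the only duration variable available to it is not cut at first BSI and can be a consequence of the event. If PN durations differ by bag type, omitting duration biases the bag effect (OR about 0.76 at 7.7 versus 10 days). If BSI also alters PN duration, adjusting for the total biases it in either direction: about 0.53 to 1.45 at 7.7 versus 10 days, with 88–100% false rejection, and about 0.78 to 1.14 at 9 versus 10 days, with 72% and 28%.

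These figures rest on a constant common hazard, assumed durations and assumed feedback from BSI to PN. With equal durations, or with no such feedback, the adjusted model is sound. A reader might infer that the bias must favour 3CBs; the documents do not support that. This is a recommended, inexpensive improvement, not proof that the planned result will be wrong.

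**What to change.** - Collect the dates of PN start, PN stop and first BSI.
- Count PN-days at risk from PN start to the earliest of first BSI, end of PN, discharge or death, and state how a BSI after the end of PN is handled.
- Pre-specify, as the key supportive analysis beside the logistic odds ratio, a Poisson model with log PN-days at risk as offset (or a cause-specific Cox model) using the same confounders.
- Report BSI per 1000 PN-days by PN type.
- Do not adjust the logistic model for PN days accrued after the BSI. Days cut at first BSI belong in the offset or on the time axis, not in the logistic model as a covariate; numerically, that would repeat the row where PN stops at BSI.
- Do not make agreement of the two analyses a condition for success. That would add a second criterion and cost power.

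The cost is SAP wording, one extra date (BSI onset) and a second effect measure to report. PN dates should be in the records already being read, and the exclusion of BSI before the third calendar day already requires BSI to be placed in time. The sample size does not change.
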